### **Adherence**

On-treatment adherence is recorded through self-reported adherence questionnaire at week 4 and week 8 (EoT) via phone contact visits, and by pill count at post-treatment week 12.

Study drug exposure and compliance will be summarised for all treated participants.

*On-treatment adherence* will be calculated by subtracting the number of missed doses from the total number of doses prescribed for therapy duration and dividing by the total number of doses prescribed for therapy duration. By pill count and self-reported questionnaire, compliance with glecaprevir/pibrentasvir will be individually calculated at the 90/90, 95/95 and 100/100 adherence levels, defined as receipt of  $\geq 90$ ,  $\geq 95$  or 100% of scheduled doses for  $\geq 90$ ,  $\geq 95$  or 100% of the scheduled treatment period, respectively.

A participant will be considered compliant if the individual receives  $\geq 95\%$  of scheduled doses for  $\geq 95\%$  of the scheduled treatment period. The percentage of compliant participants will be summarised for each arm and overall.

### **Exploratory Analysis**

Changes in quality of life data (EQ-5D-5L) and participant satisfaction will be compared at screening and post-treatment week 12 using the McNemar test (exact binomial probability).

Practitioner acceptability data will be compared at the time points of before FPFV and after LPLV at each site.

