#### **SVR12 (week 20) - All participants**

- Vital signs and physical measurements
- Return study drug
- Health outcome survey (EQ-5D-3L)
- Participant Satisfaction survey
- HCV RNA (Local Lab.)
- LFTs, FBC and biochemistry (Local Lab.)
- Pregnancy test (females of child bearing potential only)
- Adverse Events
- Concomitant medication
- Research specimen collection (Central Lab.):
  - EDTA plasma (at all sites)
  - PBMCs (at selected sub-study sites only)

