### **Health Outcomes Survey (EQ-5D-3L)**

The EQ-5D-3L health questionnaire provides a simple descriptive profile and a single index value for health status. This information can then be translated into a health utility, which can be used for cost-effectiveness analyses. The EQ-5D-3L will be completed by all participants in the clinic at screening and SVR12 (week 20).

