### **Participant Satisfaction Survey**

Participant satisfaction will be assessed via questionnaire completed by all participants at the screening visit and again following the completion to treatment at the SVR12 visit.

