#### ***Secondary endpoints:***

2. SVR12 defined as the proportion of patients with undetectable HCV RNA at 12 weeks post end of treatment (week 20) based on mITT population.
3. Proportion adherent to treatment and study visits (on-treatment adherence and early treatment discontinuation);
4. Change in health-related quality of life during treatment (measured by EG-5D-3L);
5. Resistance associated substitutions (RAS): SVR12 in participants with and without baseline RAS, and RAS distribution in participants with virological failures;
6. Patient treatment satisfaction measured by a questionnaire applied to all participants;

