### **10.3 Efficacy analysis**

The primary analysis will compare the randomised treatment arms on an ITT basis (see section 10.4). The primary efficacy endpoint is the proportion of patients with undetectable HCV RNA at 12 weeks post end of treatment. The treatment arms will be considered non-inferior if the lower limit 95% CI of the difference between the two arms does not exceed -6%. There will be no extrapolation of data for the primary endpoint. Patients with missing data will be analysed as missing equals failure. Secondary analyses will compare randomised treatment groups based on available data (mITT Population).

For all secondary endpoints simple pairwise comparisons of the randomised treatment arms will be undertaken for both the ITT and mITT populations.

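### The SAP gives quality of life and satisfaction a before-after McNemar test in place of the promised comparison of arms, and names an EQ-5D version the trial does not collect

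*SAP*

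**What the plan says.** Protocol 10.2 lists two patient-reported secondary endpoints: "Change in health-related quality of life during treatment (measured by EG-5D-3L" (the instrument name is misprinted there; the synopsis has EQ-5D-3L) and "Patient treatment satisfaction measured by a questionnaire applied to all participants". Protocol 10.3 then sets the rule for analysing them: "For all secondary endpoints simple pairwise comparisons of the randomised treatment arms will be undertaken for both the ITT and mITT populations".

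On collection, Protocol 6.2 says "The EQ-5D-3L will be completed by all participants in the clinic at screening and SVR12 (week 20" and describes the output as "a simple descriptive profile and a single index value for health status". For satisfaction it says "Participant satisfaction will be assessed via questionnaire completed by all participants at the screening visit and again following the completion to treatment"; the second completion falls at week 20. The response scale of the satisfaction questionnaire is not given.

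The SAP handles both outcomes in one sentence under Exploratory Analysis, which reads: "Changes in quality of life data (EQ-5D-5L) and participant satisfaction will be compared at screening and post-treatment week 12 using the McNemar test", in its exact binomial form. It names no yes/no split, no contrast between arms and no analysis population for either outcome.

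Elsewhere the SAP makes both outcomes secondary objectives. Table 9 lists change in patient-reported outcomes as a secondary endpoint but does not name satisfaction. The Secondary efficacy endpoints section lists neither.

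**The concern.** There are three faults and a minor inconsistency.

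- **Wrong contrast.** The protocol promises a comparison of randomised arms, but the SAP specifies a comparison of screening with week 20. Both arms receive the same eight weeks of drug, so change over that period mostly reflects what they share. Whether the monitoring strategy affects how patients feel, or how satisfied they are, is a different question. It is relevant here because the protocol's rationale expects simplified monitoring to appeal to patients.
- **Test and data do not meet.** McNemar's test applies to a paired binary variable. A profile or an index value has to be split first, and no split is defined. If it is chosen after the data are seen, so in effect is the result.
- **Wrong instrument name.** EQ-5D-5L appears once, in this SAP sentence. The protocol uses EQ-5D-3L in the synopsis, both Schedules of Assessments, 6.1 and 6.2.
- **Unsettled status (minor).** The outcomes are secondary in the protocol, in the SAP objectives and (for patient-reported outcomes) in Table 9, but sit under an exploratory heading where the analysis is described.

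**Working it through.** **1. The plan's own figures.** The documents give no power, SD or response rate for these two outcomes. Their only power figure concerns SVR12, and it reproduces: SE = √(0.96×0.04/125 + 0.96×0.04/250) = 0.0215; power = Φ(0.06/0.0215 − 1.96) = 79.8%, against about 80% stated. It plays no part in what follows.

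**2. How the SAP treats comparable outcomes.**

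| Outcome | Reporting by arm in the SAP |
|---|---|
| SVR12 | Tables 10 and 11, with a between-arm difference column |
| Compliance | Summarised for each arm (Adherence) |
| Treatment discontinuation | Arm columns, Table 13 |
| Unscheduled visits | Arm columns, Table 15 |
| EQ-5D, satisfaction | No shell in any of Tables 1 to 21; only the McNemar sentence |

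**3. What a pooled before-after test responds to.** Arm sizes (125 standard, 250 simplified) come from Protocol 10.1, and the two-sided 5% level from SAP Statistical Methods. All response rates are assumptions: 10% worsen in each arm, and the proportion improving varies.

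- McNemar: the number of changers is binomial(375, improve + worsen). Improvers among changers are tested against one half, rejecting at exact two-sided p ≤ 0.05. Identical arms were enumerated exactly; differing arms used 40,000 simulated trials.
- Between arms: score each person +1, 0 or −1. Variance v = improve + worsen − (improve − worsen)², and SE = √(v_std/125 + v_simp/250).
- Overall improvement is a weighted mean, for example (125×40% + 250×15%)/375 = 23.3%.

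| Overall improving | Arms (standard / simplified) | McNemar significant | Between-arm significant |
|---|---|---|---|
| 10% | identical | 3.8% | 5.0% |
| 10% | 20% / 5% | 3.5% | 79.8% |
| 15% | identical | 45.2% | 4.9% |
| 15% | 25% / 10% | 45.0% | 72.9% |
| 23.3% | identical | 99.4% | 4.9% |
| 23.3% | 30% / 20% | 99.5% | 35.5% |
| 23.3% | 40% / 15% | 99.5% | 96.5% |

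Hand check of the last row: net changes are 0.30 and 0.05. The variances are 0.50 − 0.09 = 0.41 and 0.25 − 0.0025 = 0.2475. SE = √(0.00328 + 0.00099) = 0.0653, so 0.25/0.0653 = 3.83 and power is Φ(3.83 − 1.96), about 97%, in line with the simulated 96.5%.

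Within each level of overall improvement the McNemar column hardly moves, whatever the arms do.

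**4. McNemar run separately in each arm.** Suppose 20% improve and 10% worsen in both arms. Exact power is 47.4% with 125 people and 80.3% with 250. The two verdicts disagree in 0.474×0.197 + 0.803×0.526 = 52% of trials although the arms are identical. Separate tests also give no between-arm estimate or CI.

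**5. What a between-arm analysis can deliver.** For an index adjusted for its screening value, the 95% half-width is 1.96×√(1/n₁ + 1/n₂)×√(1 − r²) in SD units, with r the assumed correlation between screening and week 20.

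| Pairs (standard / simplified) | r = 0.3 | r = 0.5 | r = 0.7 |
|---|---|---|---|
| 125 / 250 | 0.205 | 0.186 | 0.153 |
| 100 / 200 (20% missing) | 0.229 | 0.208 | 0.171 |

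If satisfaction is a yes/no item, the half-width is 1.96×√(p(1 − p)(1/n₁ + 1/n₂)). That is 9.8 points at p = 70% and 4.7 at p = 95%, or 11.0 and 5.2 with 20% missing.

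**The case against.** The strongest reply is that the arm comparison is left unspecified, not ruled out. Protocol 10.3 still applies, the SAP says it follows protocol version 2.0, Table 9 keeps patient-reported change as a secondary endpoint, and Statistical Methods offers t tests, chi-squared tests and their alternatives. A statistician could assemble the promised comparison from these. That is fair, and the claim goes no further than that the SAP does not carry the comparison through. But the general methods are not tied to these outcomes or to an arm contrast. The one sentence that does address them sets a different test, and an analyst would follow the specific text.

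Other points, and what stands of each:

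- **The satisfaction item may already be yes/no.** This stands as a qualification: if so, no split is needed there. The missing arm contrast remains.
- **The rates are assumed, and the SAP does not say the test is pooled.** True. The simulation only illustrates; that a paired time-point test contains no arm contrast follows from its form. Step 4 covers the per-arm reading.
- **Protocol 10.3 asks for simple comparisons in ITT and mITT, so adjustment and a single analysis depart from it.** Adjustment for the screening value is a recommendation for precision; an unadjusted difference with a CI would also meet the commitment. The single analysis is justified under Fix.
- **An index needs a stated derivation, and the protocol speaks of change during treatment while the survey is taken at screening and week 20.** Both stand, and the SAP should settle them.
- **The version slip is trivial.** It is a small correction, but the name should match the instrument collected.

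**Conclusion.** The concern holds. Followed as written, the SAP would test whether quality of life and satisfaction changed between screening and week 20, and would not estimate whether they differ between monitoring strategies, which Protocol 10.3 promises. It also names an instrument the trial does not collect and leaves the EQ-5D split undefined.

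Under the assumed rates, the chance of a significant pooled McNemar result runs from about 4% to over 99%, driven by overall improvement and almost unaffected by real arm differences of 10 to 25 points in the proportion improving. A between-arm test detects those differences in 35% to 96% of trials and rejects in about 5% when the arms are the same. These percentages rest wholly on assumed rates; the absence of an arm contrast does not.

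The consequence is limited to two secondary outcomes. The SVR12 question and its analysis are untouched. The change should be made, but the trial's main conclusion does not depend on it.

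**What to change.** In the SAP:

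1. Replace EQ-5D-5L with EQ-5D-3L. State that change runs from screening to week 20, and say how the profile is converted to the index.
2. Compare the week 20 index between arms (simplified minus standard) with a 95% CI, adjusted for the screening index, for example by ANCOVA. Adjustment for the randomisation strata is optional.
3. Compare week 20 satisfaction between arms with a named method that suits the questionnaire's scale, using the screening response where the scale allows.
4. Report the number in each arm with both assessments, and add one table shell with a between-arm difference column.
5. Keep before-after summaries descriptive and by arm, or define the yes/no split before using McNemar's test.
6. List both outcomes as secondary in Table 9.

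A separate mITT run is not needed. The post-treatment questionnaires are collected at the SVR12 visit, mITT removes only treatment completers who did not attend it, and the SAP does not impute missing data by default. Protocol 4.3 allows week 20 assessments to be done early at withdrawal. Applying the SAP's own window (from post-treatment day 70) to those questionnaires makes the observed-data sets for ITT and mITT coincide. The price is that earlier questionnaires do not count as week 20 data; their number should be reported.

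Cost: the wording of one SAP section, one Table 9 entry, one table shell and slightly more analysis. No protocol change and no new data collection.

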**Table 10. HCV RNA response during and post treatment, ITT population**

Response	Standard monitoring (N=XXX)	Simplified monitoring (N=XXX)	Difference between arms (95% CI)	P
HCV RNA <LLOQ, n (%) On treatment week 8 (end of treatment) Post treatment week 12		NA	NA	

\*Analysis tables will also be presented for the mITT, mITT-VF and PP populations

**Table 11. Treatment outcome, ITT population**

Outcome	Standard monitoring (N=XXX)	Simplified monitoring (N=XXX)	Difference between arms (95% CI)	P
SVR12, n (%)				
Virologic failure, n (%) On-treatment failure (non-response, breakthrough) Post-treatment relapse		NA NA	NA NA	
Failure for other reasons, n (%) Discontinuation Loss to follow up or missing SVR12 data				

\*Analysis tables will also be presented for the mITT, mITT-VF and PP populations

**Table 12. SVR12 in participant subgroups, ITT population**

Subgroup	Standard monitoring arm n/N (%; 95% CI)	Simplified monitoring arm n/N (%; 95% CI)
Male		
Female		
<65 years old		
≥65 years old		
BMI <30		
BMI ≥30		
HCV mono-infection		
HIV/HCV co-infection		
Genotype 1		
Genotype 1a		
Genotype 1b		
Genotype 2		
Genotype 3		
Genotype 4		
Genotype 5		
Genotype 6		
F0/F1 fibrosis		
F2 fibrosis		
F3 fibrosis		
Baseline HCV RNA ≥1,000,000		
Baseline HCV RNA ≥6,000,000		
Baseline HCV RNA ≥10,000,000		
On OST		

**Table 13. Primary reason for premature discontinuation of study drug**

Reason for premature discontinuation, n (%)	Standard monitoring arm (n=XXX)	Simplified monitoring arm (n=XXX)
Adverse event		
Non-compliance		
Withdrawal of consent		
Loss to follow up		
Other Specify - list		

**Table 14. NS3 and NS4A polymorphisms at baseline and virologic failure**

Subject ID	Genotype/subtype	Virologic failure	NS3 Variants		NS5A variants	
			Baseline	Failure	Baseline	Failure
Standard monitoring arm						
Simplified monitoring arm						

## **SAFETY ANALYSES**

All participants who receive at least one dose of study drug will be included in the safety analyses. Safety analyses will be performed overall and by treatment arm. Safety will be evaluated by assessment of clinical laboratory tests at various time points during the study, and by the documentation of AEs.

All safety data collected on or after the first dose of study drug administration up to 30 days after the last dose of study drug will be summarised.

### **Extent of Exposure**

A participant's extent of exposure to study drug will be generated from the study drug administration page of the eCRF.

### **Adverse Events**

Clinical and laboratory AEs will be coded using the Medical Dictionary for Regulatory Activities (MedDRA, [insert version](#)). System organ class (SOC), high level group term (HLGT), high level term (HLT), preferred term (PT), and lower level term (LLT) will be provided.

Events will be summarised on the basis of the date of onset for the event.

A treatment-emergent AE (TEAE) will be defined as:

- Any AEs with an onset date on or after the study drug start date and no later than 30 days after permanent discontinuation of study drug
- Any AEs leading to premature discontinuation of study drug

### **Adverse Event Severity**

Adverse events are graded by the investigator as mild (Grade 1), moderate (Grade 2), severe (Grade 3), or life-threatening (Grade 4) according to toxicity criteria specified in the protocol. The severity grade of events for which the investigator did not record severity will be categorized as "missing" for tabular summaries and data listings, and the most severe will be considered (for sorting purpose only) in data presented. For example, if an adverse event of the same type (PT) is listed more than once for an individual, the highest grade will be used to summarise severity.

### **Relationship of Adverse Events to Study Drug**

Related AEs are those for which the investigator selected "Related" ("Possibly related" or "Probably related") on the AE CRF to the question of "Related to Study Treatment." Events for which the investigator did not record the relationship to study drug will be considered to be related to study drug for summary purposes.

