## **7.2 Assessment of Adverse Events and Serious Adverse Events**

### **7.2.1 Assessment of Causality for Study Drugs and Procedures**

The investigator or designee must assess each adverse event for the following:

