#### **Relationship**

- Unlikely: An adverse event that is unlikely to be related to the use of the drug or procedures.
- Possibly: An adverse event that might be related to the use of the drug or procedures.
- Probably: An adverse event that is likely to be related to the use of the drug or procedures.

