### **10.4 Assessments of safety**

#### ***Safety endpoint:***

8. Proportion of patients with common adverse events (reported in greater than 5%).
9. Proportion of patients with at least one severe or potentially life threatening (grade 3 or 4) adverse event.
10. Proportion of patients with un-scheduled clinic visits.

Safety analyses will also be undertaken with the proportion of patients with Grade 3 or 4 adverse events, and grade adverse events will be summarised by randomised treatment group, by severity and relation to study drug. Serious adverse events will be summarised for all enrolled patients.

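### The protocol rates causality jointly for drug or procedures, but the SAP counts that rating as drug-related, so procedure events could be tabulated as treatment-related, mainly in the standard arm

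*SAP*

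**What the plan says.** Protocol 7.2.1 is headed "Assessment of Causality for Study Drugs and Procedures". It provides one scale with three levels: unlikely, possibly and probably. Each level is defined against the drug and the procedures together. Possibly is "An adverse event that might be related to the use of the drug or procedures" and probably is "An adverse event that is likely to be related to the use of the drug or procedures". The protocol has no separate rating for the drug alone.

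Protocol 10.4 then promises that adverse events "will be summarised by randomised treatment group, by severity and relation to study drug", with no mention of procedures.

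The SAP section Relationship of Adverse Events to Study Drug sets the analysis rule. It opens with "Related AEs are those for which the investigator selected", takes the possibly and probably levels as related, and locates the answer "on the AE CRF to the question of" relation to study treatment. An event with no recorded relationship "will be considered to be related to study drug for summary purposes". The SAP section Summaries of Adverse Events and Deaths uses this rule for treatment-related events, treatment-related events of Grade 3 or above, and treatment-related serious events. Tables 15 and 16 show treatment-related events by arm.

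**The concern.** The protocol and the SAP define relatedness differently. Under the protocol, a haematoma or a faint after venepuncture fits the probably level, because a procedure caused it. Under the SAP, an event at that level is drug-related. If investigators apply the protocol's definitions, the treatment-related rows would contain events that the drug did not cause.

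In most trials this would be noise shared by the arms. Here every participant takes the same drug for the same 8 weeks, and the number of clinic procedures is what the randomisation changes. Misattributed procedure events would therefore not be balanced. They would fall mainly in the standard arm, make its treatment-related rate look higher, and favour the simplified strategy. The burden of the monitoring itself, which is a real difference between the arms, would be reported as drug toxicity instead of being shown as such.

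**Working it through.** The documents state no adverse event rate, so there is no figure of the plan's own to reproduce on this point. The one design calculation is the power for SVR12, and it does reproduce. The standard error is √(0.96×0.04/125 + 0.96×0.04/250) = 0.02147, and Φ(0.06/0.02147 − 1.96) = 0.798, against a stated 80% or so. It is used here only for the arm sizes of 125 and 250.

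**Step 1: which procedures fall in the window.** The SAP section Adverse Events counts an event as treatment-emergent if it starts on or after the first dose date and no later than 30 days after the last dose. The scheduled draws come from the protocol's two Schedules of Assessments and section 6.1.

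| Scheduled draw | Standard arm | Simplified arm | In window? |
|---|---|---|---|
| Baseline (day 0) | yes | yes | yes, if the event starts on or after the first dose date |
| Week 4 | yes (plus 60 mL for PBMCs at sub-study sites) | no | yes |
| Week 8 | yes | no | yes |
| SVR12 (week 20) | yes | yes | no |

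For a full course, SVR12 is day 140 and the end of treatment is day 56. With the 14-day visit tolerance, the SVR12 draw is at least 140 − 56 − 14 = 70 days after the last dose, which is beyond the 30-day limit. That leaves 3 scheduled draws in the window in the standard arm and 1 in the simplified arm. Unscheduled visits may add bloods in either arm (protocol 6.1) and are not counted here.

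**Step 2: illustration of size.** All rates in this step are assumptions. Let b be the true drug-related rate, equal in both arms, and let q be the chance that one draw leads to an event rated possibly or probably related. Draws are taken as independent of each other and of drug events.

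- Standard arm rate: 1 − (1 − b)(1 − q)³
- Simplified arm rate: 1 − (1 − b)(1 − q)
- Excess: (1 − b)(1 − q)[1 − (1 − q)²]

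At q = 1% and b = 10%, the standard arm is 1 − 0.90×0.99³ = 12.67% and the simplified arm is 1 − 0.90×0.99 = 10.90%. The excess is 1.77 points, or 125×0.0177 = 2.2 participants.

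| q per draw | Excess at b = 10% | b = 20% | b = 30% | Extra participants of 125 |
|---|---|---|---|---|
| 0 | 0 | 0 | 0 | 0 |
| 0.5% | 0.89 | 0.79 | 0.69 | 0.9 to 1.1 |
| 1% | 1.77 | 1.58 | 1.38 | 1.7 to 2.2 |
| 2% | 3.49 | 3.10 | 2.72 | 3.4 to 4.4 |
| 5% | 8.34 | 7.41 | 6.48 | 8.1 to 10.4 |

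Excesses are in percentage points. The formula allows for participants who already have a drug-related event and so cannot be counted again.

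**Step 3: comparison with sampling error.** The standard error of the difference is √(b(1 − b)(1/125 + 1/250)). At b = 10% this is √(0.09×0.012) = 3.3 points, and at b = 30% it is √(0.21×0.012) = 5.0 points. An excess of 1.4 to 1.8 points is well inside one standard error.

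**The case against.** The best defence is that the SAP does not use the protocol scale directly. It uses the answer to a form question about study treatment, in a section about study drug. An investigator reading that question literally could rate a puncture haematoma as unlikely, and then nothing is misattributed. The form is not among the documents, so this cannot be excluded. What stands against it is that the protocol's definitions are the only ones the documents give for the possibly and probably levels, and those include procedures.

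Four further points have weight.

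- **Shared exposure.** Both arms have the baseline draw and either may have unscheduled bloods. A reader might infer that only the standard arm can have procedure events on treatment, or that the simplified arm's contribution is zero. The documents support only the narrower statement that scheduled draws after baseline are confined to the standard arm.
- **Timing of collection.** On-treatment events are elicited by phone in both arms, 1 to 2 days before weeks 4 and 8 (protocol 4.2 and 6.1), and event collection is not on the clinic lists for those weeks. A minor event after the week 4 draw would next be asked about some four weeks later, and one after week 8 at SVR12. Some would be forgotten, which probably reduces the effect.
- **Partial safeguards.** Table 16 separates phone from clinic contact, and events are tabulated by preferred term, so a named puncture-site event would be visible. But contact type shows where an event was reported, not what caused it. A week 4 draw event mentioned in the week 8 call would sit in the phone column. A term such as dizziness or nausea would not reveal its cause.
- **Limited consequence.** No hypothesis or decision rule uses relatedness, and the documents do not say that the comparison of drug-related events is meant to inform the choice of monitoring.

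**Conclusion.** The conflict in definitions is real and can be read directly from the two documents. If the protocol's definitions are applied, procedure events can enter the treatment-related rows, and with scheduled draws 3 to 1 within the window the imbalance would run against standard monitoring.

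A reader might go further and infer that the plan does inflate the standard arm's rate. The documents do not support that. It depends on how investigators answered a form that is not available, and no event rate is given. Under an assumed 1% of draws leading to a rated event and a 10% to 30% background, the excess is about 1.4 to 1.8 points, or about 2 of 125 participants. It is probably less because of when the calls are made, and zero if investigators rated the drug alone. The larger values in the table need draw-related events to be common, for which the documents give no evidence.

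Nor does the point reach the main conclusions. SVR12 is untouched, and the SAP's primary safety endpoints (common events, Grade 3 or 4 events, unscheduled visits) do not use relatedness. This is a minor point about a secondary safety summary.

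**What to change.** Reconcile Protocol 7.2.1 with the SAP's relatedness rule:

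- In the protocol and on the adverse event form, rate relation to study drug and relation to study procedures as two separate items.
- In the SAP, count an event as treatment-related only on the study-drug item. This also lets the plan deliver what Protocol 10.4 promises, a summary "by severity and relation to study drug".
- Add one row to Table 15 showing procedure-related treatment-emergent events by arm, so that the burden of monitoring is reported as such.

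If the form can no longer be changed, the existing medical monitor can classify each possibly or probably related event as drug or procedure from a listing before database lock, without the arm shown where feasible.

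The cost is one extra item per event or a short listing review, plus one table row. The downside is slightly more data entry.
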